### **13.1 Monitoring**

To help ensure that NIH/ ORSC Good Clinical Practices are being carried out, a Clinical Trials Management (CTM)/ RCHSPP designee on behalf of OCRPRO will conduct a Study Initiation Visit (SIV) prior to study enrollment beginning. The purpose of this meeting is to review with the Principal Investigator (PI) and study team their roles and responsibilities, as well as their commitment to adhere to the requirements of the protocol, especially in terms of AE, SAE and UP reporting requirements (NIH/OHSRP). In addition, the quality management and data management plans for the study will be reviewed.

## **14 Statistical Considerations**

This study is highly exploratory as very little is known about skin immunity to bites of these vectors. The simple characterization of this skin immunity will be important, as even with a small samples size we expect to be able to identify important aspects of the innate and adaptive immune response after a vector bite by examining the transcriptomic responses of differentially expressed genes. Assessing the use of next generation transcriptomic and immunohistochemistry techniques, we have made estimates that will allow us to see useful differences between bitten and unbiten skin.

### **14.1 Study Hypothesis**

The study hypothesis is that there will be differential transcriptomic gene expression and immunohistochemical differences between the cases (bitten skin) and controls (unbitten skin from the opposite arm) with regard to innate immune markers at Day 0 after the first bite of an insect in a relatively naïve individual. We also expect to see differential gene expression and immunohistochemical differences of adaptive immune markers between cases (bitten skin) biopsies collected on Day 42 and Day 44 (experienced cohort) as compared to controls (unbitten skin).

## **14.2 Sample Size Justification and Analysis Plan**

Previous studies of the skin transcriptomes have estimated approximately 13,000 genes per biopsy of healthy individuals [18]. This large number of genes will be examined to find a smaller list of differentially expressed genes within cohorts. To analyze the data, non-normalized raw counts will be used with an analysis program (e.g., the EdgeR package) to perform differential gene expression analysis after quality control of samples. Our anticipated analysis program will utilize model-based scale normalization, estimate dispersions, and apply a negative binomial model for RNA transcriptomic data analysis to find differentially expressed genes.

Single comparisons will be made within cohorts of bitten skin at a particular timepoint to the unbitten skin biopsy. Because our study will analyze paired samples (bitten skin and unbitten skin biopsies from the same individual), we can employ two different approaches. First, we can apply general linear modelling (GLM) using a GLM likelihood ratio test for comparing bitten versus unbitten skin. Also, we can employ group-wise comparisons where negative binomial fitting is followed by exact test. FDR adjustment will be used for multiple testing correction. An FDR threshold of 0.1 for statistical significance is typically applied. Genes with larger differential expression will be defined with a log-fold-change threshold of 0.5 (i.e., 50% change between experimental conditions).

Currently it is unknown how uniform skin immune responses to bites of these vector are and how much variability will be observed. Therefore it is very difficult estimate an exact samples size. As this study is very exploratory in nature it is likely with the relative small number of individuals in each cohort the results will be very informative of future studies as it will offer more insight into the diversity or lack thereof in the skin responses. The cohort sizes of 15 will allow of us to have adequate numbers to perform these detailed and expensive immunohistochemical and transcriptomic techniques that could lead to future larger studies with more focused testing once the differential genes and important areas of immune response are identified.

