### 3 Study Design

#### 3.1 Description of the Study Design

This is a single-center, case-control study of healthy skin immune response to bites of three species of colony-reared arthropods not infected with any pathogen. Healthy participants will undergo vector feeding with one of the three types of vectors as described in Table 1. Participants will be assigned to a vector in a 1:1:1 ratio. Additionally, participants will be assigned to a cohort: Cohort A will undergo a single feeding and Cohort B will undergo 4 feedings, each about 2 weeks apart.

**Table 1.** Sample size estimate per cohort and vector group.

Vector	Cohort A (Vector-Naïve)	Cohort B (Vector-Experienced)	Total
Aedes aegypti	15	15	30
Anopheles gambiae	15	15	30
Lutzomyia longipalpis	15	15	30
Total	45	45	90

After the one vector feeding for Cohort A, participants will undergo skin punch biopsy at three sites: two at the sites of bites at 2 different time points (case) and one from unbitten skin (control). After the fourth and final vector feeding for Cohort B, participants will undergo skin punch biopsy at three sites: two at the sites of bites at 2 different time points (case), and one from unbitten skin (control). Skin biopsies will be used for research tests to evaluate local immune response to vector bites. Additionally, systemic immune response will be evaluated on blood collected after the one feeding for Cohort A and after the fourth and final feeding for Cohort B.

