#### 3.2 Study Endpoints

##### 3.2.1 Primary endpoints

- Measurement of changes in the early innate immune response and cellular recruitment in the skin of bitten versus unbitten skin in each vector group in Cohort A by:

- a. immunohistochemistry of target proteins in vector-naïve participants for each of the three vector groups at 30 minutes and 4 hours after 1 feeding/exposure. Biopsies from eight participants within a group will be assigned for immunohistochemical analysis.
  - b. Transcriptomics via deep sequencing and/or gene expression array of cDNA libraries made from skin RNA of vector-naïve participants for each of the three vector groups at 30 minutes and 4 hours after 1 feeding/exposure. Biopsies from seven participants within a group will be assigned for transcriptomic analysis.
2. Measurement of changes in the adaptive immune response and cellular recruitment in the skin of bitten versus unbitten skin after fourth and final feeding in each vector group in Cohort B by:
    - a. immunohistochemistry of target proteins in vector-experienced participants for each of the three vector groups at 4 hours and 48 hours after 4 feedings/exposures. Biopsies from eight participants within a group will be assigned for immunohistochemical analysis.
    - b. Transcriptomics via deep sequencing and/or gene expression array of cDNA libraries made from skin RNA of vector-experienced participants for each of the three vector groups at 4 hours and 48 hours after 4 feedings/exposures. Biopsies from seven participants within a group will be assigned for transcriptomic analysis.

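### Section 14.2 compares each bitten time point with the one control biopsy, when one participant-blocked model on all three biopsies would give more residual degrees of freedom and a late-versus-early contrast

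*Combined protocol and SAP*

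**What the plan says.** Sections 3.1 and 7.1.3 give each participant three punch biopsies: two from bite sites at different times and one from unbitten skin of the opposite arm. The bitten times are 30 minutes and 4 hours in Cohort A, and 4 hours and 48 hours in Cohort B. For primary endpoints 1b and 2b, section 3.2.1 says: "Biopsies from seven participants within a group will be assigned for transcriptomic analysis".

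Section 14.2 gives the comparison structure in one sentence: "Single comparisons will be made within cohorts of bitten skin at a particular timepoint to the unbitten skin biopsy". It then says: "Because our study will analyze paired samples (bitten skin and unbitten skin biopsies from the same individual), we can employ two different approaches". The first approach is a likelihood ratio test from a GLM. The second is worded as follows: "Also, we can employ group-wise comparisons where negative binomial fitting is followed by exact test".

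On variability, the program will "estimate dispersions, and apply a negative binomial model for RNA transcriptomic data analysis". The section does not say which biopsies enter each fit or each dispersion estimate, gives no design matrix, and names no contrast between the two bitten times.

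**The concern.** With seven participants per group, the information for estimating gene-wise variability is scarce. The natural reading of the comparison sentence is two separate analyses, early bite against control and late bite against control, each leaving one of the three biopsies unused. The exact test compares two groups at a time and has no participant term, so it also gives up the pairing that section 14.2 has just invoked.

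Two things are at stake for endpoints 1b and 2b. One is power at the strict per-gene thresholds that follow from screening about 13,000 genes. The other is what can be said about timing. With only two gene lists, a gene found on one list alone could be described as early or late although the difference was never tested. A gene found on both could be taken as confirmed twice although both results use the same control biopsy.

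**Working it through.** The documents state no residual df, power, SD or dispersion, so there is no figure to reproduce.

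**Inputs.** From the documents: n = 7 participants per vector group and cohort (3.2.1), 3 biopsies each (3.1), about 13,000 genes and an FDR threshold of 0.1 (14.2). Assumed: a true change of 1.0 log2 units, residual SD s of 0.4 to 0.7 log2 units, and 0, 5 or 10 prior df from dispersion shrinkage.

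**Step 1: residual df per gene** (libraries minus fitted parameters).

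| Analysis | Separate pair | All three biopsies |
|---|---|---|
| Participant-blocked | 14 − (7 + 1) = 6 | 21 − (7 + 2) = 12 |
| Unpaired groups | 14 − 2 = 12 | 21 − 3 = 18 |

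The df are halved only in the paired case.

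**Step 2: a relevant threshold.** With Benjamini-Hochberg adjustment at 0.1 over 13,000 genes, the cut-off is 0.1 × k / 13,000 when k genes are declared. A cut-off of p = 0.001 corresponds to k = 0.001 × 13,000 / 0.1 = 130 genes, so 0.001 is a reasonable illustration. The two-sided critical t at 0.001 is 5.96 on 6 df and 4.32 on 12 df. At 0.05 it is 2.45 and 2.18.

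**Step 3: power.** This is a log-scale normal approximation to the negative binomial analysis. The standard error is s × √(2/7) and the noncentrality is 1.0 / (s × √(2/7)). For s = 0.5 this is 1.0 / 0.267 = 3.74. Power comes from the noncentral t with residual plus prior df, at two-sided p = 0.001:

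| s | Prior df | Separate | Joint |
|---|---|---|---|
| 0.4 | 0 | 31% | 64% |
| 0.4 | 10 | 72% | 79% |
| 0.5 | 0 | 16% | 36% |
| 0.5 | 5 | 34% | 45% |
| 0.5 | 10 | 43% | 50% |
| 0.7 | 0 | 5.3% | 12.0% |
| 0.7 | 10 | 14.7% | 17.5% |

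At p = 0.05, with s = 0.5 and no shrinkage, power is 87% against 93%.

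**Step 4: the time contrast.** In the joint model, late minus early bite also has standard error s × √(2/7), on 12 df. Its estimate does not involve the control biopsy.

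**Step 5: the shared control.** With equal residual variance s², each bitten-minus-control difference has variance 2s² and the two share covariance s². Their correlation is s² / 2s² = 0.5. This comes from having one control per participant and is the same under either analysis.

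**The case against.** The strongest reply is that section 14.2 says which comparisons are made, not which libraries enter each fit. A comparison at one time point can be a contrast from a GLM fitted to all three biopsies, in which case nothing is lost. This stands: the df loss is what the text allows and most naturally describes, not something it states. Dispersion shrinkage also narrows the gain, to 43% against 50% in the central case with 10 prior df, and the halving does not apply to the exact test.

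It is also fair that a late-versus-early test is not a stated aim. The objectives, endpoints and hypothesis are bitten against unbitten; in primary objective 2, the reference to time concerns repeated exposures. The study is described as highly exploratory, and nowhere does it say that genes will be labelled by list overlap. The missing contrast is therefore a missed opportunity, not a failure to test a declared hypothesis.

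Two stronger inferences are tempting and neither is supported.

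- *Separate fits inflate the overlap of false hits.* In a null simulation with variance estimated and no shrinkage, a gene at p < 0.001 at one time had about a 0.7% chance of p < 0.001 at the other with separate fits, and about 10.9% with the joint fit, which shares one variance estimate. Joint fitting does not reduce the overlap.
- *One odd control creates false hits at both times.* With variance estimated from the pairs, a control shifted by 4 or 8 SD lowers the false-hit rate per time point from 5% to 3.4% or 0.5%. With dispersion held fixed (assumed 0.16) and one control 4-fold or 16-fold off, false hits at both times are 4% or 11% with separate fits and 6% or 25% with the joint fit. So the joint model is no remedy for an aberrant control, and section 14.2 already plans sample quality control.

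**Conclusion.** The point stands as a cheap improvement, not as an error in the plan. Section 14.2 describes two-sample comparisons against one control biopsy and leaves the model unspecified, although each participant supplies three biopsies. If the pairs are fitted alone with participant blocking, 6 residual df are used where 12 are available. At p = 0.001, for a 1.0 log2 change and SD 0.5, the gain from joint fitting is 20 percentage points without shrinkage, 11 with 5 prior df and 7 with 10. The effect size, SD and prior df are all assumptions; the direction of the gain is the same in every setting tried, but its size depends on them.

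The late-versus-early contrast comes from the same data. The correlation of about 0.5 between the two bitten-versus-control estimates is a property of the design; it limits how overlap may be read, and changing the model does not remove it. The finding concerns the transcriptomic endpoints. Section 14.2 gives no method for immunohistochemistry, so no equivalent criticism of its fit can be made from the text.

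**What to change.** Replace the comparison sentence in section 14.2 with wording to this effect:

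- Within each vector group and cohort, one negative binomial model per gene is fitted to all three biopsies of every participant, with a participant block and a three-level factor (control, early bite, late bite).
- Three contrasts are taken from it: early bite against control, late bite against control, and late against early bite.
- A gene is called early- or late-specific only from the late-versus-early contrast. Presence on both bitten-versus-control lists is not treated as independent confirmation, because both use the same control biopsy.

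Remove the unpaired exact test as an alternative.

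The cost is a few lines of text and a different design matrix; no new samples or visits are needed. The downside is that the model assumes a common gene-wise dispersion across the three biopsies, which can be checked in the same data.

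### Section 14.2 names no primary test for the gene lists, and its likelihood ratio option on 7 pairs tends to exceed the 0.1 FDR threshold when few genes change

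*Combined protocol and SAP*

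**What the plan says.** Section 3.2.1 makes skin transcriptomics a primary endpoint in both cohorts (items 1b and 2b) and fixes the numbers: "Biopsies from seven participants within a group will be assigned for transcriptomic analysis".

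Section 14.2 gives the analysis. The unit is one time point against the control biopsy: "Single comparisons will be made within cohorts of bitten skin at a particular timepoint to the unbitten skin biopsy". The program will "estimate dispersions, and apply a negative binomial model for RNA transcriptomic data analysis to find differentially expressed genes", but the way dispersions are estimated (common, trended, gene-wise or shrunken) is not stated. Two tests are offered. One is "First, we can apply general linear modelling (GLM) using a GLM likelihood ratio test for comparing bitten versus unbitten skin". The other is "Also, we can employ group-wise comparisons where negative binomial fitting is followed by exact test". Nothing says which is primary. On error control the section says "An FDR threshold of 0.1 for statistical significance is typically applied", and it does not name the adjustment procedure. It expects about 13,000 genes per biopsy. On variability it says "Currently it is unknown how uniform skin immune responses to bites of these vector are and how much variability will be observed".

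**The concern.** The likelihood ratio test compares its statistic with a chi-square distribution as if each gene's dispersion were known. With few residual degrees of freedom the dispersion is poorly known, and some unchanged genes get extreme p-values because their dispersion was underestimated. This hardly shows at p<0.05. It shows at the very small p-values that decide membership of a list drawn from thousands of genes.

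FDR is the only error control stated for these endpoints, and section 14.2 intends the genes found to guide later, more focused studies. Excess false genes would be carried into that work. Leaving the choice between two tests open adds to this: they behave very differently, and the choice could be made after both lists have been seen.

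**Working it through.** **Inputs from the documents.** 7 pairs per vector group and cohort (3.2.1). About 13,000 genes, FDR 0.1, and one time point against control per comparison (14.2).

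**Inputs assumed, because the documents give none.** Benjamini-Hochberg adjustment. Biological coefficient of variation (BCV) about 0.3. Gene dispersions drawn as BCV² × d/χ²(d), where smaller d means more spread between genes (d = 6, 10, 40). Between-participant SD 0.4 on the log scale. 2-fold true effects in 1% to 30% of genes.

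**1. The plan's own figure.** The 0.1 is a chosen threshold. No power, sample size or achieved rate is derived from it, so there is nothing to reproduce.

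**2. Information per gene.** Libraries: 7 × 2 = 14. Coefficients: 7 participants + 1 bite effect = 8. Residual degrees of freedom: 14 − 8 = 6. Lists: 3 vectors × 2 cohorts × 2 time points = 12.

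**3. The cause.** In a Python implementation (20 runs per setting), the likelihood ratio test given the true dispersions held its level: realised FDR 0.070 to 0.102, and P(p<0.001) about 0.0010 for unchanged genes. Seven pairs with a chi-square reference are therefore not the problem by themselves. Estimating the dispersion is.

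**4. The tail.** In edgeR 4.0 with estimated dispersions, P(p<0.001) for unchanged genes was 0.0013 to 0.0036 under the likelihood ratio test and 0.0006 to 0.0010 under the quasi-likelihood F-test. Example from the Python run with 2% changed genes and d = 10: there are 13,000 × 0.98 = 12,740 unchanged genes. The nominal count below 0.001 is 12,740 × 0.001 = 12.7. At the observed rate it is 12,740 × 0.00266 = 33.9. At p<0.05 the rate was 0.051, close to nominal.

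**5. Realised FDR at nominal 0.10** (edgeR 4.0, paired design, 4 or 5 runs per setting; ranges span the dispersion spreads tried):

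| Genes changed | Likelihood ratio test |
|---|---|
| 1% | 0.13 to 0.34 |
| 5% | 0.11 to 0.17 |
| 10% | 0.10 to 0.13 |
| 20% | 0.09 to 0.10 |
| 30% | 0.07 to 0.08 |

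The quasi-likelihood F-test gave 0.06 to 0.09 at 1%, 5% and 10% changed.

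The Python runs agree. With shrunken dispersions (prior df 10), the likelihood ratio test gave 0.16 to 0.31 at 2% changed. At 10% changed it gave 0.115 to 0.135, rising to 0.170 when the base dispersion was 0.25. It held at 30% changed (0.08), and with uniform dispersions when the prior df was estimated from the data (0.087 to 0.098). The quasi-likelihood F-test gave 0.057 to 0.083 throughout.

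**6. In genes** (Python, d = 10, prior df 10). With 2% changed: about 203 called, 203 × 0.223 ≈ 45 false, against 203 × 0.1 ≈ 20 allowed. With 10% changed: about 1,092 called, about 137 false, against about 109 allowed. With no gene changed, the likelihood ratio test listed at least one gene in 95% of runs and the quasi-likelihood F-test in 10%.

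**7. The exact test**, read as unpaired. In Python its FDR was 0.001 to 0.073, except 0.146 in the harshest setting (d = 4, 2% changed). In edgeR its power was only 0.002 to 0.23 at 1% to 10% changed.

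**8. Power, likelihood ratio to quasi-likelihood, both at nominal 0.10** (edgeR). About 0.84 to 0.77 at 10% changed; 0.75–0.78 to 0.57–0.67 at 5%; as steep as 0.58 to 0.07 at 1%. At a matched realised FDR of 0.1 the two were nearly equal: 0.71 and 0.70 at 5%, 0.34 and 0.35 at 1%.

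**The case against.** The excess depends on three things the documents leave open: the share of changed genes, the spread of dispersions between genes, and the dispersion method. The upper figure of 0.34 needs only 1% of genes to change, and nothing in the documents says that so few change in bitten skin. This stands, and it is why no single figure is claimed.

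The 6 residual degrees of freedom also rest on a reading. Fitting both time points together would use 21 libraries and 7 + 2 = 9 coefficients, leaving 12, and section 14.2 does not exclude this. At d = 10 the joint fit lowered the realised FDR from 0.288 to 0.211 (1% changed) and from 0.123 to 0.110 (10% changed). It reduces the excess without removing it.

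The study is described as exploratory, and 0.12 in place of 0.10 is modest for a screening list. That is fair for the milder settings. It is weaker where few genes change, since the list is meant to steer later work.

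The quasi-likelihood test finds fewer genes. That is true at the same nominal threshold, but the matched comparison shows that most of the likelihood ratio test's extra yield comes from its looser error rate.

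Finally, section 3.2.1 allows expression arrays as well as sequencing. Count-model tests do not apply to array intensities, so this point covers sequencing counts only.

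**Conclusion.** The concern holds in a limited form. Section 14.2 leaves the primary test for the gene lists open. One option, the likelihood ratio test, is too liberal in the far tail with 7 pairs and estimated dispersions; the other, as described, gives up the pairing that the section itself invokes. The direction was the same in edgeR and in separate Python code. The size rests on assumed inputs (BCV about 0.3, 2-fold effects, Benjamini-Hochberg) and on few simulation runs: from no excess when 20% or more of genes change to roughly threefold at 1%.

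A reader might infer that the likelihood ratio test cannot hold 0.1 on 7 pairs, so the reported lists will carry more false genes than the plan claims. The documents do not support that. They say the test can be applied, not that it will be. They call 0.1 a typical threshold and claim no achieved rate. They also supply none of the inputs that decide whether an excess occurs.

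**What to change.** In section 14.2, name one primary paired test for count data: the quasi-likelihood F-test (glmQLFit and glmQLFTest in the package already given as the example), with participant as a blocking factor and Benjamini-Hochberg at 0.1. State in the same place how dispersions are estimated. If the exact test is kept, label it supportive.

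This takes a sentence or two of text and a one-line code change, with no new samples. The price is the shorter list shown in step 8 of the working, with the largest loss where very few genes change. If a longer screening list is wanted, state a higher FDR threshold openly and do not rely on a liberal test to lengthen it.

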##### **7.1.3 Skin biopsies**

From each participant, three 3-mm skin biopsies will be taken, two at the bite sites and one at an unbiten site on the opposite arm (control), using the following procedure:

1. Participant will be placed in a relaxed position with their arm out to expose the insect bites or control site on the ventral side of the appropriate forearm.
2. A time-out will take place where the participant's name and medical record number and the site of the biopsy will be confirmed. The time and date of the time-out will be documented.

3. Non-sterile gloves will be worn and pads will be laid out to protect clothing as needed.
4. Biopsy location will be marked with small circle.
5. 2% lidocaine with or without epinephrine will be drawn up in a 3-mL syringe.
6. A 30-gauge needle will be used to inject lidocaine: It will be inserted into the skin just outside the circle drawn around the biopsy site; 1-1.5 cc of lidocaine will be injected slowly.
7. Anesthesia will be tested using sharp forceps. More lidocaine will be injected as needed to achieve proper local anesthesia.
8. Chlorhexidine swabs will be used to disinfect the biopsy site by wiping concentrically from the center of the site to the outside of biopsy site.
9. A steri-drape may be applied around the biopsy site.
10. The biopsy will be performed by pulling skin taut with thumb and forefinger above and below the marked area. A punch biopsy tool will be used to apply pressure and turned back and forth 360 degrees. Forceps will be used to pull out the biopsy. Scissors may also be used if necessary to cut the specimen from the subcutaneous tissue.
11. Pressure will be held at the site using gauze, and then the site will be cleaned and dressed appropriately.
12. Sutures may be placed if deemed necessary by the clinical team. If sutures are placed, the participant will return to clinic approximately 10 days later for suture removal.

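### Section 14.2 allows an exact test that cannot use the pairing, leaves the GLM's participant term unstated and names no primary transcriptomic analysis

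*Combined protocol and SAP*

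**What the plan says.** Section 14.2 plans each test as a two-biopsy contrast: "Single comparisons will be made within cohorts of bitten skin at a particular timepoint to the unbitten skin biopsy". It then gives the design as the ground for a choice of method: "Because our study will analyze paired samples (bitten skin and unbitten skin biopsies from the same individual), we can employ two different approaches". The first is a model: "First, we can apply general linear modelling (GLM) using a GLM likelihood ratio test for comparing bitten versus unbitten skin". The second is a group comparison: "Also, we can employ group-wise comparisons where negative binomial fitting is followed by exact test". No design matrix, participant term or blocking factor is given for the model. Nothing ranks the two methods or says what happens if they return different gene lists. Significance is to be judged at an FDR of 0.1.

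Section 3.2.1 makes the assay a primary endpoint in both cohorts (1b and 2b): "Transcriptomics via deep sequencing and/or gene expression array of cDNA libraries made from skin RNA", with the allocation "Biopsies from seven participants within a group will be assigned for transcriptomic analysis". Sections 7.1.3 and 14.1 place the control biopsy on the same participant's opposite arm. Section 7.2.2 lists the assays again without a model. No correlation, dispersion or power is stated anywhere, and Section 14.2 says that variability is unknown.

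**The concern.** A group-wise negative binomial exact test compares two independent sets of libraries. It has no term for the participant, so pairing cannot be a reason for using it. A GLM can carry such a term, but without one it is also a two-group test. The plan therefore allows analyses that leave person-to-person variation in the error term, although a control biopsy is taken from every participant and would let that variation be removed.

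The result reported for endpoints 1b and 2b is a list of genes passing a threshold, drawn from 7 participants per vector group. If the permitted analyses give lists of very different length, the plan does not fix which list answers the endpoint, and the choice could be made after seeing both. Section 14.2 expects the genes identified here to focus later, larger studies, so genes that miss the cut may not be followed up.

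**Working it through.** The plan has no figure of its own to reproduce.

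**Inputs from the documents:** 7 participants per vector group and cohort (3.2.1); about 13,000 genes and FDR 0.1 (14.2).

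**Assumed, because the documents give none:** 650 genes (5%) truly changed 2-fold; mean or median count 300; dispersion 0.16 × 10/chi-square(10) by gene; within-person correlation ρ from 0 to 0.7.

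**Step 1: why pairing matters.** On the natural-log scale, take a gene with variance σ² = 0.16 + 1/300 = 0.1633 and effect ln 2 = 0.693.
- The true standard error of the mean difference is √(2σ²(1−ρ)/7): 0.216 at ρ = 0, 0.181 at 0.3 and 0.153 at 0.5.
- An unpaired analysis uses √(2σ²/7) = 0.216 whatever ρ is. Its expected statistic stays at 0.693/0.216 = 3.2.
- The paired statistic rises from 3.2 to 0.693/0.181 = 3.8 and 0.693/0.153 = 4.5.
- The price of pairing is residual degrees of freedom: 14 − 8 = 6 instead of 14 − 2 = 12.

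**Step 2: size of the unpaired test.** Under the null its statistic has standard deviation √(1−ρ). With 12 + 10 (prior) = 22 df the 5% cut-off is 2.074.
- At ρ = 0.3 the effective cut-off is 2.074/0.837 = 2.48, a size of about 2.1%.
- At ρ = 0.5 it is 2.074/0.707 = 2.93, about 0.8%.
- Simulation gave 2.2% and 0.9%. The paired test stayed at 5.0%.

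**Step 3: genes passing FDR 0.1, moderated t-test.** Log-normal simulation, Benjamini-Hochberg, 20 replicates, standard error at most 6 genes.

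| ρ | Unpaired: true genes of 650 | Paired: true genes of 650 | Unpaired: false share |
|---|---|---|---|
| 0 | 258 | 191 | 9.5% |
| 0.1 | 256 | 269 | 5.5% |
| 0.2 | 244 | 339 | 3.7% |
| 0.3 | 222 | 409 | 1.9% |
| 0.5 | 224 | 549 | 0.3% |
| 0.7 | 216 | 631 | 0% |

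The paired false share was 9–10% throughout. Repeat runs gave 222–239 against 409–418 at ρ = 0.3, 224–238 against 543–550 at 0.5, and 258–262 against 191–194 at 0. Hence the rounded 230 against 410, 230 against 545, and 259 against 191.

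**Step 4: the plan's own kind of test.** Negative binomial counts with estimated dispersions, 10 replicates.

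| ρ | Exact test (false share) | GLM, no participant term | Participant-blocked likelihood ratio (false share) |
|---|---|---|---|
| 0 | 317 (15%) | 321 | 286 (19%) |
| 0.1 | 331 (11%) | 335 | 349 (18%) |
| 0.2 | 330 (8%) | 334 | 415 (18%) |
| 0.3 | 347 (5%) | 351 | 483 (16%) |
| 0.5 | 364 (1%) | 371 | 585 (15%) |
| 0.7 | 405 (0%) | 408 | 639 (14%) |

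The GLM without a participant term is nearly the same as the exact test. Part of the blocked gain here is looser calibration; step 3 shows the gain without it. In a separate run with dispersions treated as known and 10% of genes changed 2-fold, the blocked likelihood ratio test held 7.5–9.2%. That points to dispersion uncertainty as a main source of the excess.

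**Step 5: sensitivity to dispersion.** By the step 3 method, unpaired against paired:
- dispersion 0.09: 519 against 507 at ρ = 0, and 527 against 601 at 0.3;
- dispersion 0.25: 52 against 8 at ρ = 0, and 5 against 131 at 0.3.

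**Step 6: ranking.** With each method cut at a realised false share of 10%, step 3 gives 271 against 204 at ρ = 0, 437 against 423 at 0.3, and 550 against 551 at 0.5.

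**The case against.** The strongest reply is that the GLM is introduced because the samples are paired, so the natural reading is that it is the approach that uses the pairing. The section is worded as anticipated practice, and Section 14 calls the study highly exploratory. On this view only an unwritten design matrix is missing. That has force for the GLM: a reader might infer that an unblocked model is planned, and the documents do not show this. It does not cover the exact test, which cannot use pairing, or the lack of a primary analysis. The exploratory aim lowers the stakes but does not say which list is the result.

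Step 6 is a second reply: an investigator working from ranks loses little. This stands as a limit. The plan, however, sets a threshold, and there the lists differ.

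Third, the size is conditional. Near ρ = 0 blocking loses genes. For plain gene-wise t-tests break-even lies at about 0.27–0.41; the lower value near 0.1 depends on sharing variance information across genes, which is reasonable for the kind of program Section 14.2 names. If participants also differ in how strongly they respond (natural-log SD 0.35), the gain at ρ = 0.3 remains: 129 against 303.

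Finally, a blocked likelihood ratio test ran above 10% in step 4. That is a fair criticism of simply adding a participant term, and the fix below deals with it.

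**Conclusion.** The point holds as an inconsistency and an unspecified choice that should be fixed. Samples described as paired may be analysed by a test that ignores the pairing, the GLM's participant term is unstated, and neither method is primary for endpoints 1b and 2b.

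Under the assumptions above, an unblocked analysis is conservative once ρ exceeds about 0.1 to 0.2. It then passes clearly fewer true genes, roughly 230 against 410 at ρ = 0.3. Since the documents give no ρ, the size of the loss is illustrative; at ρ near zero there is none.

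Two stronger readings should be resisted. One is that the exact test would fill the list with false genes because of ignored pairing. From ρ of about 0.2 upward its false share was 8% or less. The 15% at ρ = 0 cannot come from ignored pairing, because there is then no correlation to ignore. The other is that the planned single contrasts of one bitten timepoint with unbitten skin are at fault. They are not, and the calculations here use them.

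**What to change.** In Section 14.2, name one primary transcriptomic analysis, for example:

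> For each cohort and vector group, the primary analysis is a negative binomial GLM with participant as a blocking factor. Each bitten-timepoint versus unbitten contrast is tested with FDR adjustment at 0.1, using a test that allows for uncertainty in the dispersion estimate, such as a quasi-likelihood F-test. For array data, the equivalent linear model with participant as a block is used.

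If the likelihood ratio test is kept, state that its realised FDR may exceed 10% at this sample size (14–19% in step 4). Delete the group-wise exact test or label it a sensitivity analysis.

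The cost is wording only; no samples or visits change. The downside is some loss of genes if ρ is near zero: 191 against 258 by moderated t. Each participant gives three biopsies ("From each participant, three 3-mm skin biopsies will be taken, two at the bite sites and one" from unbitten skin), so one blocked model can use all of them: 7 × 3 = 21 libraries, 7 + 2 = 9 coefficients, 21 − 9 = 12 residual df instead of 6. In simulation this found 257 true genes at ρ = 0 and 436 at 0.3, with a false share of 9–10%, so it recovers nearly all of that loss. It does assume similar residual variability at the two bitten timepoints, so it is offered as an option.
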